4.4 Recruitment Procedures

Recruitment Procedures Survey:

Recruitment will use a multipronged approach including community advertising, social media, word of mouth and leveraging of our community partners.

1.) Onsite at barbershops, Health Living and Learning Center (HLLC) and other community partner sites: Supervised by the research team, graduate and undergraduate students will be introduced to community partners and trained to introduce the study to potential participants who visit partnership businesses and organizations across the City of Petersburg. Project personnel will have a regular, weekly presence at each community partner site to build recognition and recruit to the survey.

- 2.) Additional recruitment pathways include distribution of study advertisements. These will be posted physically at various community locations and include a URL and QR code that enable access to the survey. We will also leave study information postcards (same URL and QR code) for distribution by community partners. We will also ask community partners with email lists, regular newsletters and other similar distribution lists to send out information about the study on their listservs.
- 3.) Social Media: distribution of study and survey advertising (including a link to the survey) using various social media platforms(e.g., direct recruitment via Facebook ads, posting information on VCU, VSU, and community partner social media accounts).
- 4.) Referral of friends (snowball) participants who complete the survey will have the option of completing a quick and seamless electronic recommendation for friends or family to consider participating.
- 5) Clinic partners. We have partnered with CVHS which has 4 clinics in the Petersburg city and surrounding counties. We will advertise in the clinic waiting rooms, staff at the clinics will hand out flyers for the study, and we will use any newsletters distributed by the clinic including playing our video on the television in the waiting rooms and sending invites to learn more via the text messaging system the clinic uses to distribute public health information, updates and health messages.

4.5 Risks

Subject confidentiality will be protected by storage of all data (survey data, focus group recordings) using a unique research identification number. Data will be stored in a VCU secure database with limited, monitored access by the research team only. Identifiable information will not be collected for survey participants. We believe that the unauthorized or accidental release of study data is extremely unlikely given the precautions that will be taken to minimize such an event.

Confidentiality with focus groups will be maintained using the VCU ZOOM account, storage of the recordings on VCU secure servers with limited access by study staff only on password protected and VCU owned computers. Participants will be asked to identify themselves using any made up name they choose.

Personal discomfort is a possibility given the subject matter. If someone is uncomfortable they do not have to continue to participate or answer any survey or focus group questions that they do not want to. They can also opt to obtain assistance with navigation to screening services without participating in the study.

4.6 Anticipated Benefits

No direct anticipated direct benefits beyond learning new information about CRC prevention and screening.

The screening intervention may identify previously unknown precancerous lesions or CRC that need to be treated.

4.7 Vulnerable Populations

NA

4.8 Consent/Assent Procedures

1. We will use an information form that covers all basic elements of consent. We are requesting waiver of all elements of consent for both the survey and the focus group. The survey collects non-identifiable information about attitudes, beliefs and behaviors related to cancer prevention and CRC cancer screening. This will be collected anonymously. The focus groups are small, completed using video conferencing (VCU ZOOM) and will use pseudonyms. The content of the focus groups will be to understand what barbers think the the training needs for becoming a CRC CHamP (i.e., a community resource for information), insights about program marketing and recruitment, how COVID-19 may affect their ability and interest in participating and recruiting. The focus group evaluating the initial QR code intervention will inform the research team on how to tailor the intervention to Black men age 45-75. These are not private information. The consent form would be the only identifying information being collected for the survey participants. The survey responses will be anonymous.
2. The intervention will use a self-administered consent form that participants will complete on their own through the mHealth application (the app).

5 - Study Design

5.1 Study Design

Cross sectional survey and focus groups

Aim 3: single arm, pre-post intervention

5.2 Study Duration

36 months

5.3 Outcome Variables

Please see the survey measures

Aim 3:

Primary Outcome: CRC screening status at 3 months

Secondary Outcomes:

- Enrolment
- Viewing videos (# views, # repeat views)
- Completion of baseline, 2 week and 12 week questionnaires (retention)
- Completing values elicitation activity

- Responding to request to contact clinic/navigation services
- Sharing any content with social network

5.4 Study Procedures

Survey

The survey will be a self-administered electronic survey (e-survey) expected to take 15-20 minutes to complete. Using a secure HIPAA compliant VCU Redcap survey housed on a VCU server, a unique survey link will be provided to interested participants (via email or QR code available on flyers and social media messaging). The secure, unique link will include a screener to determine eligibility, a self-administered information form with consent elements followed by the survey. Participants who complete surveys will receive an electronic gift card of \$20 sent to an email provided by the respondent.

Focus Groups:

Local barbers currently working in a Petersburg or Richmond Barbershop; will be recruited for focus groups. Barbershops are an excellent way to gain intervention 'reach' among our target population, Black men. Barbers within the Petersburg area will be recruited from one of the four community partner barbershops that agree to participate in the study. Barbers will be approached in-person at the shop by a member of the research team) who will visit shops to introduce the study and ask permission to leave study information and/or come back to talk to the group. Focus groups will be conducted virtually using smartphone accessible VCU Zoom and will be video recorded, with permission. Participants will engage in a 60-90-minute discussion.

Aim 3 Intervention:

Men will be invited to participate using all methods outlined above. Men who are interested will be directed to download the app to their personal device. Once the app is downloaded participants are able to self-direct through the screening process. If requested, a study member can assist with downloading the app and navigating through to the study screener.

Potential participants will be asked to complete a screener to ensure all eligibility criteria are met. Those who do not meet eligibility will be thanked for their time and navigated to an exit screen. For those who are eligible, they will next be asked to complete the consent process. After they consent, they will be navigated to the baseline questionnaire. Once completed, they will be able to access all other content (videos, infographics, request link to receive a call from screening navigation, additional surveys for values elicitation).

One week after enrollment, men who have not engaged with the materials, completed the baseline questionnaire, or the navigation request will receive a text message aligned with the CRC risk perception and/or values elicitation that they shared with us at baseline. See table below.

Question: Which best describes your thoughts about colorectal cancer?

PARTICIPANT RESPONSE	AUTOMATED, TAILORED ANSWER
Never heard of it	Video # may interest you because it talk about CRC is and why screening can save your life!
Heard of it but not interested in screening	You might be interested to hear about the experiences of a CRC survivor. Video xx is “name” telling his story.
Heard of it and thinking about getting screened	You may want to check out video #, because it goes over the different types of screening options. The best one is the one that gets done!
Decided not to get screened	You might be interested to hear about the experiences of a CRC survivor. Video # is “name” telling his story. Video # also describes the many different screening options.
Decided to get screened	Inside the app there is a way to ask for a local clinic or screening navigator to call you directly. Check it out!
Have been screened in the past, but not recently	The best CRC screening test is the one that gets done! You may be interested in talking to a screening navigator. Inside there is a way to request a phone call from a local clinic.

Follow up: A three months after enrollment men will receive the final survey in their app and a text message notifying them that it is ready to be completed. Anyone who does not complete this survey within two weeks will be contacted by telephone by a study team member and given the option to complete it over the phone, have it emailed to them or to complete it in the app.

Table 2. Measures for intervention

Timing	CRC risk perception	Demographics	Health literacy (1 item)	Reg source of primary care	Health status	Intention to screen	Screen status	CRC knowledge	Medical mistrust
Baseline	X	x	x	x	x	x	x	x	x
2 weeks	X				x		x	x	
12 weeks	X				x	x	x		

5.5 Withdrawal Procedures

Participants can exit the browser at any time for both the survey and focus groups. Once the data has been collected participants will not be able to have their data erased (surveys are collected anonymously).

To withdraw from the intervention participants must contact one of the study PIs in writing.

5.6 Locations/Facilities

All study procedures will occur online

5.7 Data Collection

The survey will be a self-administered electronic survey (e-survey) expected to take 15-20 minutes to complete. Using a secure HIPAA compliant VCU Redcap survey housed on a VCU server, a unique survey link will be provided to interested participants (via email or QR code available on flyers and social media messaging).

Focus Groups: Participants (n=16) will be barbers employed at one of the four community partner barbershops. Two virtual focus groups of 6-8 barbers will be conducted. Focus groups will be conducted virtually using smartphone accessible VCU Zoom and will be video recorded, with permission. Participants will receive a \$20 honorarium for the 60-90-minute discussion.

Intervention: Baseline, 2 and 12 week follow up surveys will be collected on the app. If men do not respond to the follow up survey on the app they will be contacted by a study team member and provided alternatives for completion (see study procedures above).

5.8 Data Collection Sources

Survey Measures. The survey has been designed to obtain key information while minimizing participant burden. *Demographics:* age, sex, highest attained education, annual household income, employment status, and marital status; health literacy (1 item); health status (1 item).

Medical Mistrust. measures (1) suspicion, (2) group (racial) disparities in health care, (3) lack of support from health care providers.

Perceived Racial Discrimination. Everyday Discrimination Scale reflect day-to-day experiences of unfair treatment. Higher scores corresponded to more frequent experiences of racial discrimination;

Preventive health care behaviors: The Good Health Practice Scale,⁶³ a 16-item scale that measures key preventive health behaviors. This scale has been shown to assess the avoidance of preventive health behaviors.

Social Support: MOS-SSS aims to assess the extent to which a person has the support of others to face stressful situations.

CRC Test fear and invasiveness and Cultural Attitudes about Masculinity: Males Role Norms Inventory-Short Form (MRNI-SF) is a 21-item questionnaire that assesses conformity to dominant cultural norms of masculinity (avoidance of femininity, negativity towards sexual minorities, self-reliance through mechanical skills, toughness, dominance, importance of sex, restrictive emotions). High total scores indicate greater conformity to traditional norms of masculinity

CRC Risk Perceptions. Lifetime risk of developing CRC will be asked on a 0-100% scale and a likert response adapted from the NIH HINTS.

Colorectal Cancer Screening Behaviors. Assessed using questions vetted by the national Behavioral Risk Factor Surveillance System we will measure those who have ever been screened and those who are up-to-date with screening

Focus Group: A focus group interview guide has been developed to inform how the barbers can be engaged to introduce the intervention, be empowered to have conversations about the need for CRC screening among Black men and encourage men to engage with the QR code and intervention materials.

Intervention.

1. Measures. See Table 2 above for all measures and timing of collection for the intervention.
 - a. Outcomes measures
 - i. CRC screening status (>60%) **OR**
 - ii. Intention to screen (>80%): from S2S
 - b. Covariates
 - i. Perceived CRC risk: *CRC Risk Perceptions.* Lifetime risk of developing CRC will be asked on a 0-100% scale and a likert response adapted from the NIH HINTS
 - ii. CRC knowledge: from S2S
 - iii. Medical mistrust: *Medical Mistrust.* measures (1) suspicion, (2) group (racial) disparities in health care, (3) lack of support from health care providers.
 - iv. Value elicitation
 - v. Health Literacy-1 item
 - vi. Regular source of primary care -1 item

vii. Health status -1 item

Demographic information: age, highest attained education, annual household income, employment status, and marital status; family history of cancer)

2. User engagement data collected from Pattern Health to determine the number times, number of minutes and which content pieces were interacted with in the app environment.
 - a. Enrolment
 - b. Videos viewed (# views, # repeat views)
 - c. Completion of baseline and follow up questionnaires (retention)
Completing values elicitation activity
 - d. Responding to request to contact clinic/navigation services
 - e. Sharing any content with social network

5.9 Standard Tools

See survey measures for complete list

6 - Statistical Analysis

6.1 Sample Size

The survey component was powered on the interaction term "discrimination*preventive care engagement", both continuous, using a simulation study of 1000 runs of a logistic regression model, with the binary screening behavior response (1 = screened, 0 = not screened). A sample size of 175 subjects generates 80% power to detect a "small to moderate" effect size of 0.38 (corresponding odds ratio = 2.01, using R package "effect size") for the interaction term (continuous*continuous), at 5% level of significance, using a one-sided Z-test. To account for individuals who start but do not complete the survey we have added a buffer of 20% which gives a sample size of n=210 for the survey.

We will also conduct focus groups with n=16 men.

Total project sample size n=226

Intervention Sample Size: To perform an initial test of efficacy, satisfaction and feasibility, we will test the intervention on 30 men.

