3.2 Hypothesis

H1.1. Lack of social support, higher medical mistrust, and perceived discrimination will be negatively associated with self-reported guideline concordant screening behaviors.

H2.2. Higher engagement in preventive care behaviors and greater perceived risk will be associated with higher completion of CRC screening. Subaim1a. Examine potential interactions between perceived discrimination, medical mistrust and engagement in preventive care behaviors.

H1.3. Increased perceptions of discrimination and greater medical mistrust will attenuate the relationship between preventive care and guideline concordant screening.

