4.2 Number of Participants

We require 8-10 men for the Community Advisory Board and we require n=175 Black or African American for survey in PART1. The intervention component will require n=30 men

Total study n=225

The survey component was powered on the interaction term "discrimination*preventive care engagement", both continuous, using a simulation study of 1000 runs of a logistic regression model, with the binary screening behavior response (1 = screened, 0 = not screened). A sample size of 175 subjects generates 80% power to detect a "small to moderate" effect size of 0.38 (corresponding odds ratio = 2.01, using R package "effect size") for the interaction term (continuous*continuous), at 5% level of significance, using a one-sided Z-test. To account for individuals who start but do not complete the survey we have added a buffer of 20% which gives a sample size of n=210 for the survey. The sample size has been chosen for the intervention to support an initial examination of intervention effectiveness using a one-arm design. This is a typical size that will generate pilot data on the feasibility of our approach.

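### The survey's power statement pairs 0.38 with an odds ratio of 2.01 by a conversion that does not fit a continuous interaction; the 80% cannot be confirmed, and on the natural scoring the odds ratio points away from H1.3.

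*Combined protocol and SAP*

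**What the plan says.** Section 6.1 makes the interaction of discrimination with preventive care engagement the basis of the survey size: "The survey component was powered on the interaction term", with both variables continuous. The power was obtained "using a simulation study of 1000 runs of a logistic regression model", for a "binary screening behavior response (1 = screened, 0 = not screened").

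The result is given as "A sample size of 175 subjects generates 80% power to detect" a small-to-moderate "effect size of 0.38 (corresponding odds ratio = 2.01"), tested "at 5% level of significance, using a one-sided Z-test". Section 4.2 repeats the sentence.

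Section 3.2 states the direction of the interaction in H1.3: "Increased perceptions of discrimination and greater medical mistrust will attenuate the relationship between preventive care and guideline concordant screening". H2.2 in the same section expects more preventive care to go with more screening. Section 5.8 says that higher discrimination scores mean more frequent discrimination. It does not give the scoring direction of the preventive-care scale. Section 6.2 tests parameters at 5% without saying one- or two-sided.

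Neither 4.2 nor 6.1 gives the screening prevalence, main effects, predictor SDs or scaling, predictor correlation, covariates, or the direction of the one-sided test.

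**The concern.** Two features of the power sentence do not fit the model it describes.

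- **Scale.** An effect size and an odds ratio are presented as equivalent, but the link between them belongs to a comparison of two group means. For a product of two continuous predictors, 0.38 and 2.01 are different effects, and their power at n=175 differs widely.
- **Sign.** H1.3 predicts that discrimination weakens a positive association. With 1 = screened, that is normally an interaction odds ratio below 1. The plan quotes one above 1 and a one-sided test.

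The target of 175 (210 with the buffer) rests on this sentence. As written, a reader cannot tell whether the survey is sized for an odds ratio of 1.46 or 2.01, or which direction of interaction the test could declare significant.

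**Working it through.** **Inputs from the plan:** n=175, power 80%, one-sided 5%, effect size 0.38, odds ratio 2.01, 1 = screened (6.1); H1.3 and H2.2 (3.2); discrimination scoring (5.8).

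**Inputs assumed, because the plan gives none:** predictor SD of 1 unless stated, and a range of prevalences, main effects, correlations and covariates.

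**1. How 0.38 and 2.01 are linked.** The conversion from a standardised mean difference d is OR = exp(d·π/√3).
- exp(0.38·π/√3) = 1.99.
- In reverse, ln(2.01)·√3/π = 0.385.
- The pair agrees within rounding under this conversion.
- Read as a logistic coefficient, exp(0.38) = 1.46, while ln(2.01) = 0.698.
- The two coefficients differ by a factor of 0.698/0.38 = 1.84.

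**2. Reproducing the 80% in closed form.** For independent predictors with SD 1 the product has variance 1, and

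power = Φ(β·√(n·p(1−p)) − 1.645).

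At p = 0.5, √(175 × 0.25) = 6.614.
- β = 0.38: Φ(2.513 − 1.645) = 80.7%. At p = 0.6 it is 79.3%, at p = 0.7 it is 74.5%.
- β = 0.698: Φ(4.617 − 1.645) = 99.9%. At p = 0.2 or 0.8 it is 98.0%.

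So the closed form comes near 80% for a coefficient of 0.38, and not for an odds ratio of 2.01 on this scale. The plan, however, says that its figure came from simulation.

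**3. Simulation.** Logistic model with intercept, both main effects and the product; Wald Z-test; n=175; SD-1 normal predictors unless stated.

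| Effect per SD × SD | Setting | One-sided 5% | Two-sided 5% |
|---|---|---|---|
| OR 2.01 | about 30–70% screened | about 97–99% | 94–98% |
| Coefficient 0.38 (OR 1.46) | about 30–70% screened | about 67–79% | 55–68% |
| Coefficient 0.38 | independent, no main effects, 50% screened | about 75% | about 63% |
| Coefficient 0.38 | correlation 0.5 / 0.6, no main effects | 80% / 81% | 68% / 69% |
| Coefficient 0.38 | uniform SD-1 predictors | 79% | not run |
| Coefficient 0.38 | main effects −0.4 and +0.4, 0 or 8 covariates, 44–68% screened | 63–71% | 50–59% |

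Section 3.2 predicts non-zero main effects, so the last row is closer to the plan's own hypotheses than the rows without them. At 50% screened with independent normal predictors and no main effects, 80% one-sided power needs about 70–80 men for OR 2.01 and about 200 for a coefficient of 0.38.

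**4. What would bring OR 2.01 to 80% at n=175.**
- Predictor SD 0.75 gives 77%, SD 0.77 gives 81%, SD 0.80 gives 87%.
- About 90–92% screened gives 83–76%.
- With 76% screened, main effects of −0.7 and +0.7 and 6 covariates, power falls to 85%.

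**5. Sign.** H2.2 makes the preventive-care coefficient positive. If discrimination weakens it, the coefficient falls as discrimination rises, so the product coefficient is negative and its odds ratio is below 1. The mirror image of 2.01 is 1/2.01 = 0.50. A test in the correct tail has essentially the same power there (about 99%), and about 75% for −0.38. A one-sided test in the opposite tail rejected in at most 0.03% of runs for −0.38 and in none for 0.50.

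**The case against.** A reader might infer that the 80% fails on every reading. The documents do not support that. For a coefficient of 0.38, the closed form and some simulated settings come to about 80%; for an odds ratio of 2.01, predictor SDs near 0.77 do so. Standardisation is my assumption, since the plan says only that both variables are continuous. This objection stands: the fault is an effect stated on an unsuitable scale with the inputs left out, and a failed calculation has not been shown.

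A reader might also infer that the survey is underpowered. That follows only if 0.38 was the simulated coefficient and the inputs were unfavourable. If 2.01 per SD × SD was meant, the stated 80% is conservative.

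On direction, a reader might infer that the final analysis has no chance of supporting H1.3. That requires an upper-tailed final test, and section 6.2 states no side. The quoted odds ratio may be only a magnitude, the sub-aim in 3.2 is to examine interactions without a direction, and reversing the sign does not change n. Section 5.8 describes the preventive-care scale as able to assess avoidance; if it is scored that way, the sign problem lapses.

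The small-to-moderate label sits beside 0.38, where it is coherent as a mean difference. It is part of the conversion problem and not a further error.

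What survives is that the conversion does not describe the tested term, that the two figures imply clearly different power on a standardised scale, and that sign and tail are unstated where they matter.

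**Conclusion.** The point holds in this form. The effect that supports n=175 is given as two figures that are not the same logistic interaction. On a standardised scale at ordinary prevalence, the stated 80% fits an odds ratio of 2.01 poorly and lies at or above the upper end of what a coefficient of 0.38 gives. One explanation is that 0.38 was simulated as a coefficient and then converted as if it were a mean difference; that is an inference and the plan does not say so. Because the inputs are missing, the 80% can be neither confirmed nor refuted.

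The direction part is conditional on higher scores meaning more engagement and on a one-sided test in the direction of the quoted odds ratio. Under those conditions the test could not support H1.3. It is a matter of stating the hypothesis and tail correctly, with no effect on the sample size.

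The sponsor should correct this. Confidence is moderate, because the size of the discrepancy depends on inputs that the plan does not report.

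**What to change.** Keep n=175 and restate the calculation.

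- Re-run the simulation with the interaction odds ratio expressed per SD × SD and in the direction of H1.3 (below 1 if higher scores mean more engagement).
- State the assumed screening prevalence, main effects, predictor correlation, covariates and the scoring direction of both scales.
- Choose one sidedness and, if one-sided, one direction, and write the same choice in 6.1 and 6.2.
- Quote the resulting power, or the odds ratio detectable with 80% power, in both 4.2 and 6.1.
- Remove the 0.38 figure and its small-to-moderate label.

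The cost is a re-run of an existing simulation, the same sentence edited in two sections and a line added to 6.2. No extra participants are needed. The price is that the quoted power or detectable effect may look less favourable, particularly if the test is two-sided or realistic main effects are included.
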